### **Other Outcome Measures:**

- spontaneous opioid craving, assessed using the Penn Alcohol-Craving Scale, as modified to assess opioid craving
- affect, assessed using the Positive and Negative Affect Schedule (PANAS)
- anxiety assessed by State subscale of the Spielberger State-Trait Anxiety Inventory
- blood pressure, heart rate, and respiratory rate during the laboratory sessions
- Plasma levels of CBD
- plasma levels of buprenorphine

**Participant Recruitment:** Patients will be recruited from the Tarzana Treatment Center in the San Fernando Valley (TTC), where buprenorphine or methadone (as part of their treatment) and CBD (as part of this protocol) will be administered.a Tarzana Treatment Centers, Inc. is a community-based, private non- profit behavioral healthcare organization located in Southern California with several agency sites, including the one in the San Fernando Valley, where this protocol will be conducted.

TTC delivers drug and alcohol use treatment, has been accredited by the Joint Commission on Accreditation of Healthcare Organizations (JCAHO) since 1987, and has a workforce that includes physicians, psychologists, and nurses. TTC's substance use treatment approach includes residential programs that are overseen by a Program Director and are staffed by a clinical supervisor, operations supervisor, counselors, interns, nursing staff and 24/7 technicians. Groups and services include education group, process group, 12-step, family group, mental health services and recreation skills. Cognitive-behavioral treatment is used in both individual and group therapy to address craving and relapse issues and in the treatment of mental health problems.

**Randomization to Treatment:** Up to 60 patients who meet all eligibility criteria will be randomized to receive CBD or placebo (up to 30 patients per group): CBD 600 mg/day (300 mg twice daily). Within each cohort, patients will be randomized by baseline plasma buprenorphine level (either below or  $\geq$  2 ng/mL)

**Dosing and Testing Schedule:** The study will comprise three periods: a 14-day screening period while patients are stabilized on buprenorphine), a 28-day treatment period (CBD 600 mg/day or placebo), and a 28-day follow-up period after termination of treatment with medication.

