Laboratory sessions using a craving cue-induction paradigm will be conducted before dosing on Day 0 (baseline) and on Days 7 and 28 after adjunctive treatment with CBD.

Note: Participants will all be maintained on buprenorphine or methadone, which are robust, effective treatment for OUD that diminish cravings, and helps to protect participants if relapse occurs. Thus, conducting cue reactivity tests in the presence of opioid agonist medication is inherently less risky than in individuals with untreated OUD. Total scores  $> 70$  on the Desire for Drug Questionnaire (scores ranging from 14 to 98) will be reassessed after participants remain in study visit area for 15 min and again at 30 min if the score remains above 70. Research staff will check in with participants to provide support and resources as requested, or to coordinate care with current clinical staff at TTC.

Adherence to medication in the trial will be assured as the patient will take the test medication (CBD or placebo) under supervision. Blood samples will be collected to determine plasma concentrations of CBD and its metabolites (7-hydroxy CBD and 7-carboxy CBD), buprenorphine and methadone and their metabolites as well as the endocannabinoids anandamide and 2-AG, which may contribute to the response to CBD and laboratory assessments of safety. Retention in treatment (this trial plus buprenorphine + naloxone) will be assessed over the 28-day medication (CBD or placebo) treatment period and weekly follow-up assessments for the subsequent month (28-day follow-up period).

**Duration of Treatment and Dropout.** Duration of inpatient treatment with buprenorphine or methadone (outside the scope of this protocol) is generally for about one month at the Tarzana Treatment Center (TTC), and buprenorphine or methadone is often continued after a client leaves TTC. The treatment phase of this study of CBD vs. placebo is 28 days. If a participant decides to stop taking buprenorphine or methadone and/or leave TTC before completing the 28-day intervention described in this protocol, they will be withdrawn from the study and will receive compensation for the portion of the study that they completed.

**Number of Patients Planned:** Approximately up to 60 patients will be recruited.

- The active treatment group will include up to 30 patients receiving CBD (600 mg/day).
- The control group will include up to 30 patients receiving placebo.

---

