**Key Exclusion Criteria (see Table 2 below):**

**Table 1. Inclusion criteria**

• Ability to read and speak English and has provided written informed consent.
• Age of 18-65 years (inclusive).
• Meeting criteria for an OUD according to the MINI for $\geq 3$ months before screening.
• Self-report of opioid use in the 30 days before screening; verified by treatment center records.
• On a stable dose of $\geq 12$ mg buprenorphine, either alone, or in combination with naloxone (buprenorphine/naloxone ratio of 4/1) or methadone for at least 7 days prior to starting and for the duration of the treatment phase of the study.
• If female, being surgically sterile or willing to use birth control (e.g., oral contraceptives, condoms, intrauterine device) or willingness to abstain from sex throughout the study.
• Body Mass Index (BMI) between 17.5 and 35 kg/m  ; total body weight $> 110$ lb (50 kg).
• Currently in residential treatment at the Tarzana Treatment Center.

Patients will be excluded for physiological dependence on alcohol or a sedative-hypnotic drug, requiring medical detoxification, receiving medication-assisted treatment with naltrexone, and showing signs of acute opioid withdrawal symptoms (score of 5 on the Clinical Opiate Withdrawal Scale, COWS).

Because Cue-induced craving for opioids will be a secondary outcome, participants will be screened to eliminate those who do not report sufficient craving in response to visual cues (pictures). Those who do not have a craving score of at least 50 (on a visual analogue scale with a maximum score of 100) for at least one image within one category (groups of images may be separated into smoking cues, pills and bottles, and injection paraphernalia). For example, for injection cues, a picture of a needle and syringe may elicit a craving response, though other images in the same group (i.e., picture of arm with vein bulging) do not elicit craving.

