### 3. Study Overview

#### 3.1. Study Design, Blinding, and Randomization

This is a randomized, double-blind, placebo-controlled, phase 2 trial to evaluate the safety and efficacy of CBD as adjunctive therapy in patients receiving medication-assisted inpatient treatment for OUD. It is a single-site study, conducted at a residential treatment center. The original plan was for ~60 subjects to be randomized (2:1 CBD:placebo) for study in two ascending dose cohorts, the first receiving CBD 600 mg/day orally (PO) (n = 20) or placebo (n = 10) and the second receiving CBD 1200 mg/day PO (n = 20) or placebo (n = 10), ultimately creating three equal arms. Due to budgetary constraints, the higher-dose cohort was eliminated, and the randomization ratio was reversed to 2:1 placebo: CBD 600 mg/day towards the end of the lower-dose segment of the study to balance the remaining two arms as much as possible. This SAP is based on data from 28 participants randomized using a 2:1 CBD 600 mg/placebo ratio and 7 participants randomized using a 2:1 placebo:CBD 600 mg ratio.

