From May 2022 through May 2023, 28 participants were randomized 2:1 CBD 600 mg:placebo; however, 6 of these participants did not receive any study drug.

Towards the end of enrollment of the first dose cohort, it became clear that financial constraints would preclude study of a higher dose cohort. In June 2023, randomization was reversed to 2:1 placebo:CBD to increase power by balancing the low CBD and placebo groups as much as was

possible in the remaining time. From June 2023 through January 2024, 7 participants were randomized 2:1 placebo:CBD 600 mg. This SAP is based on the study plan that includes these modifications. It is expected that there will be 21 patients in the 600-mg CBD arm ( $28*0.67+7*0.33$ ), and 14 patients in the placebo arm ( $28*0.33+7*0.67$ ).

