### 3.4. Objectives and Endpoints

Objectives	Endpoints
Primary: To evaluate the safety and tolerability of CBD in the study population.	Primary: Number of treatment-emergent adverse events over the 28-day treatment period by study arm. Secondary: Changes in liver enzymes, pulse oximetry, sedation, and cardiovascular measures (heart rate, blood pressure, and cardiac rhythm and conduction on EKG).
Secondary: To determine the extent to which CBD (600 mg/day) reduces cue-induced craving for opioids relative to placebo.	Primary: Cue-induced craving for opioids, assessed using the Desires for Drug Questionnaire (DDQ)  in the context of an opioid cue-induction paradigm, assessed in the laboratory session before CBD dosing on Day 0 (baseline without CBD) and on Days 7 and 28 (after adjunctive treatment with CBD) Secondary: Spontaneous opioid craving, assessed using the Penn Alcohol-Craving Scale, as modified to assess opioid craving;  affect, assessed using the Positive and Negative Affect Schedule (PANAS),  Anxiety, assessed by state subscale of the Spielberger State-Trait Anxiety Inventory,  Percentage of patients with increase in their buprenorphine dose, Treatment retention, as indicated by number of days of continued participation
Exploratory: A. To evaluate effects of CBD on metabolism of other endocannabinoids, i.e., N-arachidonylethanolamide (anandamide) and 2-arachidonoyl-glycerol (2-AG) levels. B. To assess pharmacokinetics of CBD in patients receiving buprenorphine for treatment of OUD.	Plasma levels of anandamide and 2-AG. CBD pharmacokinetics—time to reach steady state and accumulation parameters (C max , AUC 0-24 ). In addition, the buprenorphine/norbuprenorphine ratio will be determined to evaluate potential drug-drug interactions of CBD with buprenorphine metabolism (dealkylation). Although this ratio does not, by itself, an increase in the ratio, concurrent with the emergence of hypoxia and/or sedation would be an AE.

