## **5. Analysis Populations (Analysis Sets)**

The randomized population will include all subjects randomized regardless of whether they had any study drug.

The safety population will include all subjects who received at least one treatment of study drug and will be used for the summaries of all baseline, demographic, and safety data.

The full analysis set (FAS) population is a subset of safety population and consists of those that have at least one post-baseline efficacy measurement. This population will be used for the summaries of all efficacy data.

The pharmacokinetic (PK) population is a subset of the safety population and consists of those who have at least one PK assessment.

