### **Primary Efficacy Target**

**Desire for Drug Questionnaire (DDQ):** The DDQ is a 14-item scale used to assess cue-induced craving, administered here in the context of a laboratory-based opioid cue-induction paradigm. All responses are scored on a Likert scale from "strongly disagree" (1) to "strongly agree" (7). A table will be provided with summaries per visit (Baseline, 7, and 28 days), as well as absolute and percent changes from baseline, for the DDQ Total Score of Opiate Use (subscale including 7 items, primary endpoint) and the DDQ Total Score (all 14 DDQ items, secondary endpoint), both of which will be used to assess cue-induced craving, our primary efficacy target. For each outcome, we will run a mixed model for repeated measures (MMRM), with change from baseline as the outcome; fixed effects for treatment, time, and a treatment by time interaction; and an appropriate random effects/covariance structure to account for within-subject correlations. In addition, figures, based on the MMRMs will be provided: 1) by treatment, and 2) for the difference between treatments, both with 95% model estimate confidence intervals. The primary efficacy outcome is the MMRM model estimate for change from baseline in cue induced craving at 28 days between the two treatment groups.

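### The primary efficacy MMRM for DDQ change omits the Day 0 DDQ score as a covariate, which probably gives up precision in an analysis set of at most 29 patients

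*SAP*

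**What the plan says.** SAP section 11 sets out one model for both DDQ scores (the 7-item subscale as primary endpoint, the 14-item total as secondary). It is a mixed model for repeated measures "with change from baseline as the outcome; fixed effects for treatment, time, and a treatment by time interaction", plus a within-subject covariance structure that is left open. The primary efficacy outcome is the Day 28 treatment contrast from that model.

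SAP section 3.4 confirms that the DDQ is "assessed in the laboratory session before CBD dosing on Day 0 (baseline without CBD) and on Days 7 and 28", so a pre-treatment score exists for every patient who can contribute a change score. Neither document adds it to the model as a covariate. The only covariate the SAP names is body weight, in the pharmacokinetic interaction analysis of section 12.

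Three passages bear on the number of patients:
- SAP section 3.1 reports that, among the first 28 randomised, "6 of these participants did not receive any study drug".
- SAP section 5 makes the Full Analysis Set a subset of dosed patients that "consists of those that have at least one post-baseline efficacy measurement".
- Protocol, Duration of Treatment and Dropout, says of patients who stop their opioid agonist medication or leave the centre early that "they will be withdrawn from the study and will receive compensation for the portion of the study that they completed".

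**The concern.** Taking change from baseline as the outcome assumes that each extra point of Day 0 DDQ carries forward as a full point at Day 28. If the true slope is below 1, as regression to the mean usually makes it, the change score over-corrects, and chance differences between arms at Day 0 add noise to the contrast. Estimating the slope removes that noise. The loss of precision and the chance imbalance are one problem seen from two sides, not two separate harms.

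With at most 29 patients, and possibly fewer at Day 28, a covariate that is already collected can noticeably change the width of the confidence interval for the main efficacy result.

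**Working it through.** **Inputs from the documents.** SAP section 3.5: d = 1.0, one-sided alpha 0.025 (equivalent to 0.05 two-sided), 21 CBD and 14 placebo, stated power 0.80. SAP section 3.1: 28 + 7 = 35 randomised, 6 of the first 28 undosed. Ceiling of the Full Analysis Set: 35 − 6 = 29.

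**Assumptions.** The correlation rho between Day 0 and Day 28 DDQ, the ratio s = SD(Day 28)/SD(Day 0), and the arm split of the 29 are not in the documents. If the undosed patients fell in proportion to allocation, 22 of the first 28 were dosed:
- CBD: 22 × 2/3 + 7 × 1/3 = 14.67 + 2.33 = 17.0
- placebo: 22 × 1/3 + 7 × 2/3 = 7.33 + 4.67 = 12.0

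**Step 1: the plan's own figure.** For a two-sample t-test, the noncentrality is d / √(1/n₁ + 1/n₂).
- 21:14: 1/√(1/21 + 1/14) = 2.898, 33 df, power 0.803. This reproduces the stated 0.80.
- 17:12: 1/√(1/17 + 1/12) = 2.652, 27 df, power 0.725.
- 12:8 (an illustrative 20 patients with Day 28 data, completers only): 2.191, 18 df, power 0.545.

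**Step 2: effect of estimating the slope.** For the Day 28 contrast in large samples,

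Var(adjusted)/Var(change score) = s²(1 − rho²) / (1 + s² − 2·rho·s).

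With s = 1 this is (1 + rho)/2. The difference between the two variances is proportional to (1 − rho·s)², so with many patients adjustment cannot lose. With few it pays for one degree of freedom and for chance imbalance in the covariate, a factor of about 1 + 1/(N − 4) = 1.04 on the variance at N = 29. At s = 1 and rho = 0.5 the variance ratio is 0.75 × 1.04 = 0.78, so the standard error is √0.78 = 0.88 of the planned model's.

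**Step 3: power with the Day 0 score added.** Noncentral t with N − 3 df, averaged over chance imbalance with 1 − R² ~ Beta((N − 2)/2, 1/2). In every row d = 1.0 is measured on the change-score SD, as in the SAP.

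| Split, s | No covariate | rho 0.3 | 0.5 | 0.7 | 0.8 | 0.9 |
|---|---|---|---|---|---|---|
| 17:12, s = 0.8 | 0.725 | 0.942 | 0.911 | 0.885 | 0.879 | 0.894 |
| 17:12, s = 1 | 0.725 | 0.874 | 0.824 | 0.775 | 0.752 | 0.729 |
| 17:12, s = 1.25 | 0.725 | 0.807 | 0.755 | 0.716 | 0.707 | 0.729 |
| 12:8, s = 1 | 0.545 | 0.702 | 0.640 | 0.587 | 0.563 | 0.541 |
| 12:8, s = 1.25 | 0.545 | 0.621 | 0.566 | 0.528 | 0.520 | 0.541 |

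At 17:12 and s = 1 the standard error is 0.82, 0.88, 0.94, 0.97 and 0.99 of the planned model's across the five correlations.

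**Step 4: where adjustment loses.**
- 17:12, s = 1: above rho of about 0.92, by at most 1.1 points (rho up to 0.97).
- 17:12, s = 1.25: between rho of about 0.64 and 0.89, by at most 1.8 points.
- 12:8: break-even at rho of about 0.88 (s = 1) or 0.60 (s = 1.25), with a largest loss of 2.5 points.

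**Step 5: sensitivity to the split.** At s = 1 and rho = 0.5, power rises from 0.641 to 0.747 at 21:8, from 0.694 to 0.797 at 19:10, and from 0.737 to 0.835 at 15:14. Simulation of the 17:12 and 12:8 cases agrees with the table to within 0.4 points.

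**The case against.** A change-score MMRM is a recognised analysis. It is pre-specified apart from the covariance structure, and nothing in the documents promises baseline adjustment, so no commitment is broken. The stakes are limited too: safety is the primary objective, SAP section 2 calls the efficacy information preliminary, and no decision rule depends on the DDQ p-value. This stands, and it is why the point is a recommended improvement and not an error.

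The size of the gain rests on quantities the documents do not give, and equal SDs flatter it. At s = 1.25 the changes at rho 0.3, 0.5 and 0.7 are +8.2, +3.0 and −0.9 points. At s = 1.5 they are about +4, −0.2 and −1.7. This also stands: the gain could be close to nil. The possible loss, however, stays small throughout.

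Two technical cautions are fair:
- Holding d at 1.0 on the change-score SD means a different raw effect at each correlation. With equal SDs it is √(2 × 0.7) = 1.18 baseline SDs at rho 0.3 and √(2 × 0.1) = 0.45 at rho 0.9. Adjusted and unadjusted power may be compared at one rho, but a row should not be read as one effect under varying correlation.
- The calculation matches an unstructured MMRM with complete data. With a random-intercept structure, or with missing Day 28 values where Day 7 contributes, it is an approximation.

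**Conclusion.** The concern holds. The omission is plain from the text, and the ceiling of 29 follows from the SAP. With 29 patients and equal SDs, adding the Day 0 score gains about 5 to 15 points of power at correlations of 0.3 to 0.7. At 0.5 it restores roughly the 0.80 that the SAP computed for 35 patients. Against that, the loss is at most about 2 points with 29 patients and 2.5 with 20, over the values checked. The direction is therefore probable, while the amount depends on an unknown correlation and SD ratio. Confidence is medium.

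The finding is about precision only. It does not say that either model is free of bias. SAP section 3.1 states that "the randomization ratio was reversed to 2:1 placebo: CBD 600 mg/day towards the end of the lower-dose segment", so on the assumed split about 2.33/17 = 14% of CBD and 4.67/12 = 39% of placebo patients come from after the reversal, and the Full Analysis Set excludes patients after randomisation. Freedom from bias also needs no time trend and non-informative exclusions, which baseline DDQ does not by itself secure.

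**What to change.** Before unblinding, amend SAP section 11 so that both DDQ models include the Day 0 score of the scale being analysed and its interaction with time. Keep the present model as a sensitivity analysis. The cost is SAP wording and one degree of freedom for the Day 28 contrast. No patient is lost, because a change score already needs the Day 0 value. The downside to accept is the small loss of power described above if the correlation turns out to be high or the Day 28 SD larger than at baseline.

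A secondary option, for consistency with the randomisation and not for precision, is a single term for the plasma buprenorphine stratum (below 2 versus 2 ng/mL or more). If it is not prognostic it costs 0.1 point when balanced, 1.5 to 1.8 points on average under chance imbalance, and about 4 points if it explains 10% of treatment assignment (0.824 to 0.782 at rho 0.5). Two conditions apply:
- Protocol Table 1 admits patients on buprenorphine "or methadone for at least 7 days prior to starting and for the duration of the treatment phase of the study", so methadone patients need a stated category or they would drop out of the model.
- The Protocol says "patients will be randomized by baseline plasma buprenorphine level", whereas SAP section 3.1 also names daily buprenorphine dose. Add dose only if the randomisation records confirm that it was a stratification factor.

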## 2. Background

Opioid Use Disorder (OUD) is a public health emergency leading to unprecedented drug-related mortality in the United States, underscoring the need for innovative medical treatments. Three medications are FDA-approved for treatment of OUD, but retention in treatment is low even with medication. Positive findings from preclinical and clinical studies provide a rationale for the use of cannabidiol (CBD) in treatment of OUD. Notably, a Phase 2, randomized, double-blind, placebo-controlled, pilot study found that a single dose of CBD (400 or 800 mg) decreased cue-induced opioid craving and blunted anxiety. Still, rigorous clinical trials are needed to establish the value of CBD as adjunctive therapy for OUD.

Based on prior work, CBD is expected to be well-tolerated and safe in patients with OUD, but safety signals (vital signs and laboratory test results) will be assessed in more detail here. Specifically, because CBD inhibits cytochrome P450 isozymes including CYP3A, the primary mechanism for hepatic buprenorphine N-dealkylation, we will evaluate whether CBD poses potential safety concerns associated with buprenorphine treatment. Specifically, we will seek to evaluate the frequency and magnitude of this possible drug-drug interaction to ensure safe and effective treatment of OUD for patients receiving medication-assisted treatment with buprenorphine. In addition to assessing safety, this study will provide preliminary information on the efficacy of CBD compared with matched placebo as an adjunctive treatment in patients receiving medication-assisted treatment for OUD.

Beyond the safety and efficacy objectives, prior research indicated that CBD increases fatty acid amide hydrolase, the principal enzyme catalyzing catabolism of the major endocannabinoids anandamide and 2-AG. More recent work, however, indicates that CBD inhibits anandamide uptake into cells. As such, CBD administration may affect plasma concentrations of these endocannabinoids. Plasma levels of anandamide and 2-AG will be assayed to explore whether CBD increases their concentrations in this study.

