## 4. Statistical Considerations

### 4.1. General Considerations

All key data collected on case report forms will be presented in the data listings and will be listed and sorted by treatment arm, participant number and (where applicable) visit. All descriptive summaries will be presented by treatment group and (where applicable) nominal visit/time point.

All safety and descriptive summaries will be presented by treatment group. All disposition and concomitant medication descriptive summaries will be presented by treatment sequence and nominal visit/time point (where applicable).

Unless otherwise stated, the following methods will be applied:

- **Continuous variables:** Descriptive statistics will include the number of non-missing values (n), arithmetic mean, standard deviation (SD), median, minimum and maximum values.

The minimum and maximum values will be displayed to the same decimal precision as the source data, the arithmetic mean, SD and median values will be displayed to one more decimal than the source data for the specific variable.

95% Confidence Intervals (CIs), mean differences (among treatments and from baseline) and least-square (LS-Means) values will be displayed to one more decimal than the source data for a specific variable. P-values will be displayed to 3 decimal places.

The appropriate precision for derived variables will be determined based on the precision of the data on which the derivations are based, and statistics will be presented in accordance with the afore-mentioned rules.

- **Categorical variables:** Descriptive statistics will include counts and percentages per category. The denominator in all percentage calculations will be the number of participants in the relevant analysis population with non-missing data, unless specifically stated otherwise. Percentages will be displayed to one decimal place. Proportions will be displayed to 3 decimal places.

95% Confidence Intervals (CIs), difference in proportions, odds ratios and other categorical parameters will be displayed to one decimal place for percentages. Proportions will be displayed to 3 decimal places. P-values will be displayed to 3 decimal places.

No inferential statistics will be produced for any safety endpoints.

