## 14. Timing of the Analysis

No interim analysis is required. The final analysis will be performed after database lock and unblinding.

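### The randomisation ratio was reversed from 2:1 to 1:2 in June 2023, but the primary DDQ model has no term for it, so about 22–25% of any difference between the two phases in 28-day change enters the treatment estimate

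*SAP*

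**What the plan says.** SAP section 3.1 describes two allocation phases: "28 participants randomized using a 2:1 CBD 600 mg/placebo ratio and 7 participants randomized using a 2:1 placebo:CBD 600 mg ratio". The first ran from May 2022 to May 2023 and the second from June 2023 to January 2024. On the switch it says "In June 2023, randomization was reversed to 2:1 placebo:CBD", the aim being to bring the arms closer in size after the higher-dose cohort was dropped. It adds that "28 participants were randomized 2:1 CBD 600 mg:placebo; however, 6 of these participants did not receive any study drug". The expected arm sizes are 21 CBD and 14 placebo; actual counts by phase and arm are not given.

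Section 11 (Primary Efficacy Target) models change from baseline in DDQ with "fixed effects for treatment, time, and a treatment by time interaction" and a covariance structure for repeated measurements within a subject. The treatment difference in change at Day 28 is named as the primary efficacy outcome, and section 3.5 bases the sample size on it.

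The randomisation strata in section 3.1 are plasma buprenorphine level and daily buprenorphine dose. No section uses allocation phase as a covariate, stratum or sensitivity analysis, and section 13 lists no changes to the planned analysis.

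**The concern.** Treatment was randomised within each phase, but the chance of receiving CBD was about 2/3 early and 1/3 late. Once the phases are pooled without conditioning on phase, enrolment period is associated with treatment by design. This is not chance imbalance, and its expected size would not shrink in a larger trial with the same phase proportions. Time in the model means Day 7 or Day 28, so it absorbs nothing about when a participant enrolled.

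If the 28-day change differed between the early and late periods for any reason unrelated to CBD, part of that difference would be reported as a treatment effect. The affected quantity is the only comparison the SAP powers. The reach is limited: DDQ serves the secondary objective, the SAP says that "this study will provide preliminary information on the efficacy of CBD compared with matched placebo", and for the primary safety objective "No inferential statistics will be produced for any safety endpoints".

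**Working it through.** **The plan's own figures.** Expected arms: 28 × 2/3 + 7 × 1/3 = 21 CBD and 28 × 1/3 + 7 × 2/3 = 14 placebo, as stated. Power at d = 1.0: noncentral t with 33 df and noncentrality 1/√(1/21 + 1/14) = 2.90 gives 0.803, matching the stated 0.80.

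**Share of a phase difference that enters the estimate.** Let τ be the late-minus-early difference in mean 28-day change, and s the late share of an arm. The pooled CBD-minus-placebo estimate has expectation (true effect) − τ × (s_placebo − s_CBD). The bracket is the leak.

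- All 35 randomised: s_CBD = 2.33/21 = 0.111; s_placebo = 4.67/14 = 0.333; leak 0.222.
- 29 dosed (22 early, 7 late; assumes the 6 undosed split 2:1 and all 7 late participants were dosed): s_CBD = 2.33/17 = 0.137; s_placebo = 4.67/12 = 0.389; leak 0.252.
- If the 6 undosed were all CBD, the leak is 0.178; if all placebo, 0.472.

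The dosed figure is closer to the analysis population, because section 5 restricts efficacy to dosed participants with a post-baseline measurement.

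**Bias.** With an assumed τ of 0.5 SD: 0.5 × 0.222 = 0.11 SD and 0.5 × 0.252 = 0.13 SD. The pooled standard errors are √(1/21 + 1/14) = 0.345 and √(1/17 + 1/12) = 0.377, so the bias is about one third of a standard error, or 11–13% of the planning effect.

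**Error rate.** Simulated least squares on the Day 28 change with complete data, no true effect, nominal 2.5% one-sided, 15 CBD and 7 placebo early. Entries are the rejection rate in the biased direction, with simulation error of about 0.1–0.2 percentage points.

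| Late CBD/placebo | Leak | τ = 0.25 SD | τ = 0.5 SD | τ = 1.0 SD |
|---|---|---|---|---|
| 3/4 | 4/11 − 3/18 = 0.197 | 3.3% | 4.0% | 5.2% |
| 2/5 | 5/12 − 2/17 = 0.299 | 3.7% | 5.3% | 8.7% |
| 1/6 | 6/13 − 1/16 = 0.399 | 4.3% | 7.0% | 14.2% |

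With a phase term the rate is about 2.5% in every cell. The two-sided totals without it are milder at 3/4 (5.2% at 0.5 SD, 5.6% at 1.0 SD) than at 2/5 (6.2% and 8.9%). If each late assignment were an independent 1/3 draw (an assumption; the method is not stated), 3/4 or 2/5 would occur 56% of the time and 1/6 20%.

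**Cost of adjusting.** Pooled variance is 1/n_CBD + 1/n_placebo. Phase-adjusted variance is 1/Σ[c·p/(c + p)], summed over phases, where c and p are the CBD and placebo counts in a phase.

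- 35 randomised: 0.1190 pooled; 1/(6.222 + 1.556) = 0.1286 adjusted; ratio 1.080, SE 3.9% larger; power 0.803 to 0.772.
- 29 dosed: 0.1422 pooled; 1/(4.889 + 1.556) = 0.1552 adjusted; ratio 1.092, SE 4.5% larger; power 0.725 to 0.686.
- Whole-number late splits (15/7 early): SE 2.6% larger at 3/4, 6.5% at 2/5, 13% at 1/6.

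**Break-even.** The pooled estimate has the smaller mean squared error when τ is below √(adjusted variance − pooled variance)/leak: √0.00952/0.222 = 0.44 SD (randomised) or √0.01302/0.252 = 0.45 SD (dosed).

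**The case against.** The harm is conditional. Nothing in the documents shows that the 28-day change differed between phases. Because the outcome is change from baseline, a drift that moves baseline and Day 28 equally cancels. At 0.25 SD the inflation is small, and below about 0.44–0.45 SD the pooled estimate is the more accurate one on average, so adjustment pays a certain 3–4 points of power against a hypothetical bias. On this view, keeping the pooled model as primary and adding an adjusted sensitivity analysis would be enough. With only about two late CBD participants expected, adjustment also gives back part of what the reversal was meant to gain. The 22–25% figure is itself an expectation at planned ratios.

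Most of this is correct and limits the weight of the point. It does not remove it. The size of τ is unknown in advance, and only the model that conditions on phase holds the error rate whatever τ turns out to be. Phase is also the unit within which treatment was actually randomised, so conditioning on it follows the design rather than taste. Conditions were not visibly constant: enrolment went from 28 in 13 months to 7 in 8 months, and the protocol version the SAP cites dates from the month of the switch. Neither fact shows a shift in outcome.

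**Conclusion.** The concern holds. As written, the primary efficacy analysis pools two periods with opposite allocation ratios and does not condition on period, so about 22% (randomised) to 25% (dosed) of any phase difference in the 28-day change passes into the treatment estimate. The algebra is certain; the consequence depends on a phase shift whose existence, size and direction are unknown. At an assumed 0.5 SD the bias is about one third of a standard error, and the one-sided error is 4.0–7.0% across the late splits examined. The leak depends on arm counts by phase that the documents do not report, and loss before Day 28 would move it further. The error rates come from a complete-data Day 28 comparison, not from the full two-visit model with dropout. The descriptive safety analysis is not affected inferentially. This should be fixed, because the correction is simple and its cost is modest at the expected counts.

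**What to change.** In SAP section 11, add allocation phase (2:1 CBD:placebo versus 2:1 placebo:CBD) as a fixed effect in the primary DDQ model, with phase-by-visit if it can be estimated. State the fallback now: phase main effect alone if the interaction cannot be fitted. Acknowledge that this fallback removes only about half of a shift confined to Day 28, whereas phase-by-visit removes it fully. Report the pooled estimate without phase as a sensitivity analysis, tabulate arm counts by phase and by Day 28 completion, and record the change in section 13. The same main effect may be added to the other between-arm models where the data allow.

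The choice must be fixed before database lock, since "The final analysis will be performed after database lock and unblinding" and choosing between two estimates after that would not be credible. Phase is known from each randomisation date, so no unblinding is needed.

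The drafting cost is a few sentences. The statistical cost at expected counts is the 4–4.5% larger standard error shown above. It grows if late CBD data are sparse: with 15/7 early and five late placebo participants at Day 28, the standard error is about 11% larger with one late CBD participant and about 18% larger with none. In the latter case the late placebo participants add little to the Day 28 comparison, and the report should say so.
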